10.15 Appendix 15: Sampson Criteria Questionnaire

Anaphylaxis is highly likely when any of the following 3 criteria is fulfilled (Sampson et al, 2006):

1. Acute onset of an illness (minutes to several hours) with involvement of the skin, mucosal tissue, or both (eg, generalized hives, pruritus or flushing, swollen lips-tongue-uvula)

AND AT LEAST ONE OF THE FOLLOWING

- a. Respiratory compromise (eg, dyspnea, wheeze-bronchospasm, stridor, reduced peak expiratory flow [PEF], hypoxemia)
 - b. Reduced blood pressure [BP] or associated symptoms of end-organ dysfunction (eg, hypotonia [collapse], syncope, incontinence)
2. Two or more of the following that occur rapidly after exposure to a likely allergen for that patient (minutes to several hours):
 - a. Involvement of the skin-mucosal tissue (eg, generalized hives, itch-flush, swollen lips tongue-uvula)
 - b. Respiratory compromise (eg, dyspnea, wheeze-bronchospasm, stridor, reduced PEF, hypoxemia)
 - c. Reduced BP or associated symptoms (eg, hypotonia [collapse], syncope, incontinence)
 - d. Persistent GI symptoms (eg, crampy abdominal pain, vomiting)

Reduced blood pressure after exposure to known allergen for that subject (minutes to several hours): Systolic BP of less than 90mmHg or greater than 30% decrease from the subject's Baseline systolic BP value.

AST	Aspartate Aminotransferase
ATC	Anatomical Therapeutic Chemical
BLQ	Below the Lower Limit of Quantification
BMI	Body Mass Index
BUN	Blood Urea Nitrogen
CI	Confidence Interval
CKD-EPI	Chronic Kidney Disease Epidemiology Collaboration
COVID-19	Coronavirus Disease 2019
CRF	Case Report Form
CSR	Clinical Study Report
C-SSRS	Columbia-Suicide Severity Rating Scale
CTCAE	Common Terminology Criteria for Adverse Events

CV	Coefficient of Variation
DILI	Drug-Induced Liver Injury
ECG	Electrocardiogram
eCRF	electronic Case Report Form
eGFR	estimated Glomerular Filtration Rate
EOS	End of Study
EQ-5D-5L	5-Level European Quality of Life 5 Dimensions
ES	Enrolled Set
ER	Emergency Room
FAS	Full Analysis Set
FDA	Food and Drug Administration
geoCV	Geometric Coefficient of Variation
GI	Gastrointestinal
gMG	Generalized Myasthenia Gravis
HbA1c	Hemoglobin A1C
hCG	Human Chorionic Gonadotropin
HLGT	High Level Group Term
HLT	High Level Term
ICH	International Council for Harmonisation
ICU	Intensive Care Unit
IDMC	Independent Data Monitoring Committee
IEC	Independent Ethics Committee
Ig	Immunoglobulin
IGRA	Interferon Gamma Release Assay

IMP	Investigational Medicinal Product
INR	International Normalized Ratio
IPD	Important Protocol Deviation
IRB	Institutional Review Board
IVIg	Intravenous Infusion of Immunoglobulin G
LDH	Lactate Dehydrogenase
LLOQ	Lower Limit of Quantification
LPFD	Last Patient First Dose
LPLV	Last Patient Last Visit
MA	Markedly Abnormal
MAP	Managed Access Program
MedDRA	Medical Dictionary for Regulatory Activities
MG	Myasthenia Gravis
MG-ADL	MG-Activities of Daily Living
MG-C	MG-Composite
MG-QOL15r	Myasthenia Gravis-Quality of Life
MuSK	Muscle-specific Kinase
Nab	Neutralizing Antibody
OLE	Open-label Extension
PD	Pharmacodynamics
pDILI	Potential Drug-Induced Liver Injury
PEOT	Premature End of Treatment
PEX	Plasma Exchange
pIDMC	Program Independent Data Monitoring Committee

PK	Pharmacokinetic
PMDA	Pharmaceuticals and Medical Devices Agency
PRO	Patient-Reported Outcome
PT	Preferred Term
PTT	Partial Prothrombin Time
QMG	Quantitative Myasthenia Gravis
QW	Weekly
RBC	Red Blood Cell
RLZ	Rozanolixizumab
SAP	Statistical Analysis Plan
SC	Subcutaneous
SCIg	subcutaneous immunoglobulin
SD	Standard Deviation
SGOT	Serum Glutamic-Oxaloacetic Transaminase
SGPT	Serum Glutamic-Pyruvic Transaminase
SOC	System Organ Class
SS	Safety Set
SU	Safety Update
TB	Tuberculosis
TEAEs	Treatment-Emergent Adverse Events
TEMA	Treatment-Emergent Markedly Abnormal
TFLs	Tables, Figures and Listings
ULN	Upper Limit of Normal
VAS	Visual Analogue Scale

WBC White Blood Cell

WHODD World Health Organization Drug Dictionary

1 INTRODUCTION

The purpose of this statistical analysis plan (SAP) is to provide all information that is necessary to perform the statistical analyses of study MG0007, including three interim cuts and final analysis. It also defines the summary tables, figures and listings (TFLs) to be included in the final Clinical Study Report (CSR) according to the protocol.

This SAP is based upon, and assumes familiarity with, the following documents:

- Protocol Amendment 3: 03 Oct 2022
- Rozanolixizumab Program Safety Analysis Plan: 16 Nov 2023

If a future protocol amendment necessitates a substantial change to the statistical analysis of the study data, this SAP may be amended accordingly. Changes to the analysis from the protocol are documented in [Section 3.9](#). The content of this SAP is compatible with the International Council for Harmonisation (ICH)/Food and Drug Administration (FDA) E9 Guidance documents.

2 PROTOCOL SUMMARY

2.1 Study objectives

2.1.1 Primary objective

To assess the safety and tolerability of additional 6-week treatment cycles with rozanolixizumab in study participants with generalized myasthenia gravis (gMG)

2.1.2 Secondary objective

To assess the efficacy of 6-week treatment cycles with rozanolixizumab in study participants with gMG

2.1.3 Other objectives

- To assess the pharmacokinetics (PK) of rozanolixizumab
- To evaluate the incidence and emergence of antidrug antibody (ADA) of rozanolixizumab
- To assess the pharmacodynamics (PD) of rozanolixizumab
- To assess the effects of rozanolixizumab on the concentration of [REDACTED]
[REDACTED]
- To assess the need for gMG medications including changes in type and doses
- To assess the effect of rozanolixizumab on [REDACTED]
[REDACTED]

2.2 Study endpoints

2.2.1 Safety endpoints

2.2.1.1 Primary safety endpoints

- Occurrence of treatment-emergent adverse events (TEAEs)
- TEAEs leading to withdrawal of investigational medicinal product (IMP)

2.2.1.2 Other safety endpoints

- Occurrence of serious TEAEs
- Occurrence of treatment-emergent adverse events of special monitoring (AESM)
- Vital sign values and changes from Baseline (Day 1) (systolic and diastolic blood pressure [BP] and pulse rate at each scheduled assessment during Treatment and Observation Periods)
- 12-lead electrocardiogram (ECG) values and change from Baseline at each scheduled assessment during the Treatment and Observation Periods
- Laboratory values and changes from Baseline at each scheduled assessment during the Treatment and Observation Periods (hematology, clinical chemistry, and urinalysis)

2.2.2 Efficacy endpoints

2.2.2.1 Secondary efficacy endpoints

For each of the first 3 x 6-week treatment cycle, change from Baseline (Day 1) to Day 43^a:

- In MG-Activities of Daily Living (MG-ADL) score within one treatment cycle
- In Quantitative MG (QMG) score within one treatment cycle
- In MG-Composite (MG-C) score within one treatment cycle
- In MG Symptoms patient-reported outcomes (PRO) 'Muscle Weakness Fatigability' score within one treatment cycle
- In MG Symptoms PRO 'Physical Fatigue' score within one treatment cycle
- In MG Symptoms PRO 'Bulbar symptoms' score within one treatment cycle
- In MG-ADL responder (≥ 2.0 -point improvement) within one treatment cycle
- Time to MG-ADL response (≥ 2.0 -point improvement from Baseline [Day 1]) within one treatment cycle

For consecutive treatment cycles:

- Time between consecutive treatment cycles

2.2.2.2 Other efficacy endpoints

For each 6-week treatment cycle and Observation Period (where applicable), improvement from Baseline (Day 1) to each scheduled assessment:

- MG-ADL responder (≥ 2.0 -point) within one treatment cycle
- QMG responder rate (≥ 3.0 -point) within one treatment cycle
- MG-C responder rate (≥ 3.0 -point) within one treatment cycle
- Time to MG-ADL response (≥ 2.0 -point) within one treatment cycle
- Minimal symptom expression (MG-ADL score of 0 or 1) at any time during Treatment and Observation Periods

For each 6-week treatment cycle and Observation Period (where applicable), change from Baseline (Day 1) to each scheduled assessment:

- In MG-ADL score within one treatment cycle
- In QMG score within one treatment cycle
- In MG-C score within one treatment cycle
- In MG Symptoms PRO 'Muscle Weakness Fatigability' score within one treatment cycle
- In MG Symptoms PRO 'Physical Fatigue' score within one treatment cycle
- In MG Symptoms PRO 'Bulbar symptoms' score within one treatment cycle

For each 6-week treatment cycle and Observation Period (where applicable), change from Baseline (Day 1) to Day 43^a:

- In 5-level European quality of life 5 dimensions (EQ-5D-5L) within one treatment cycle
- In Myasthenia Gravis-Quality of Life (MG-QOL15r) within one treatment cycle

Note:

^a Day 43 = Visit 8 for the initial fixed cycle and Visit 7 for the subsequent cycles.

2.2.3 Pharmacokinetic and pharmacodynamic

2.2.3.1 Pharmacokinetic endpoints

Plasma concentrations of rozanolixizumab at each scheduled assessment

2.2.3.2 Pharmacodynamic endpoints

For each 6-week treatment cycle and Observation Period (where applicable):

- Minimum value and maximum decrease from Baseline (Day 1) in total serum IgG and IgG subclasses concentration over time
- Change from Baseline (Day 1) in serum IgG subclasses concentration over time
- Change (absolute and percentage) from Baseline (Day 1) in MG-specific autoantibodies at each scheduled assessment during the Treatment and Observation Periods

2.2.4 Anti-drug antibody endpoints

- ADA at each scheduled assessment

2.2.5 Immunological endpoints

- Change from Baseline (Day 1)^b in [REDACTED] in participants experiencing infusion reactions

For initial fixed treatment cycle only:

- Change from Baseline (Day 1) in serum Ig concentrations [REDACTED] at each scheduled assessment during Treatment and Observation Periods

Note:

^b Baseline will be used from the sample collected at Day 1 (Visit 2) in MG0003. Other exploratory safety biomarkers may be assessed.

2.2.6 **Rescue therapy and healthcare endpoints**

- Use of rescue therapy (yes/no)
- Time to rescue therapy
- Healthcare resource utilization, including hospitalization (type: intensive care unit [ICU]/non-ICU and duration in each respective type of care)

2.2.7 **COVID-19 related endpoint**

- [REDACTED]

2.3 **Study design and conduct**

[figure not shown]
2.3.1 **Overall design**

This is a Phase 3, multicenter, 2-arm, OLE study to evaluate 6-week treatment cycles of rozanolixizumab in study participants with gMG. MG0007 is an extension study of MG0003. The study is open to study participants from MG0003 and MG0004.

Eligible study participants from MG0003 will be randomized to receive an initial fixed 6-week treatment cycle of a subcutaneous dose of rozanolixizumab equivalent to approximately 7mg/kg or 10mg/kg weekly (QW) (see [Figure 2–1](#) and [Figure 2–2](#)), followed by an Observation Period that begins after the last dose of that treatment cycle as per assessments described in the Schedule of Activities in protocol.

Eligible study participants from MG0004 who have completed at least 6 scheduled visits for rozanolixizumab treatment and the Premature End of Treatment (PEOT) visit can move directly into the Observation Period in MG0007. Additionally, eligible study participants from MG0004 who are in the Observation Period can complete the End of Study (EOS) visit and move directly into the Observation Period in MG0007 (see [Figure 2–1](#) and [Figure 2–2](#)). If IMP treatment was withheld for low IgG in MG0004, study participant's missed dose(s) can be counted as part of the total 6 visits for completion of MG0004 and meet eligibility requirements for MG0007. These study participants will undergo their first MG0007 treatment with rozanolixizumab upon worsening of gMG symptoms. Participants will continue on their last treatment dose from MG0004. Dose adjustments may be applied in future cycles as per description below.

The rollover into MG0007 must be completed within 4 weeks after the EOS visit from MG0003, or the PEOT or EOS (as appropriate) visit from MG0004. In the event a study participant has a gap period (>4 weeks) between the EOS or PEOT visit from the lead-in study and the start of MG0007, a Screening Period of up to 4 weeks will be applicable to confirm that the study participant still meets the eligibility criteria for entry into MG0007.

Figure 2-1: MG0007 entry schema

[figure not shown]
In case of symptom worsening (eg, an increase of 2.0 points on the MG-ADL or 3.0 points on the QMG scale) between assessments, resulting in a need for additional treatment, study participants will undergo another 6-week treatment cycle followed by an Observation Period, based on the Investigator's discretion. The dose may be adjusted to 7mg/kg or 10mg/kg at the beginning of each treatment cycle based on the Investigator's discretion. The minimal time to start the next treatment cycle is 4 weeks following the last dose of the treatment period of the previous cycle. If a study participant requires treatment earlier than 4 weeks, IgG levels from the previous cycle should be considered and discussed with the Medical Monitor. A new treatment cycle **should not** be initiated until total IgG level is $\geq 2\text{g/L}$.

Participants in MG0007 will remain on their gMG background medications. With the exception of corticosteroids and acetylcholinesterase (AChE) inhibitors, all gMG medication doses should be maintained during each respective 6-week treatment cycle and efforts should be made to maintain a stable dose during the first 8 weeks of the Observation Period.

Study participants who receive rescue therapy (intravenous immunoglobulin [IVIg], plasma exchange [PEX], subcutaneous immunoglobulin [SCIg], or iv corticosteroid) during the Treatment Period are not eligible to receive any further treatment with rozanolixizumab. These participants must complete the first 8 weeks of the Observation Period after the last dose of rozanolixizumab prior to completing the EOS visit assessments, and subsequently will be withdrawn from the study.

Those patients who received rescue therapy (IVIg, PEX, SCIg, or iv corticosteroid) during the observation or no treatment with rozanolixizumab periods may continue in the study at the Investigator's discretion and after discussion with Medical Monitor and/or UCB Study Physician. The following cycle of rozanolixizumab should in general not start earlier than 4 weeks following the last dose of IVIg, SCIg, or iv corticosteroids or the last PEX session, unless there is a medical reason, and an earlier treatment initiation is being considered [REDACTED] for the study participant as agreed upon with the Medical Monitor and/or UCB Study physician.

Study participants (not withdrawn from the study) will continue in the study and until product approval or until transition to a managed access program (MAP), if available, as indicated per the Sponsor, and according to local guidance.

Figure 2–2: MG0007 study schema

2.3.2 Dosing

This OLE study will continue treatment with rozanolixizumab subcutaneous (sc) fixed doses across body weight tiers equivalent to approximately 7mg/kg and 10mg/kg administered QW for 6-week treatment cycle (Table 2–1). Weight-based dose adjustments should be limited to a maximum of every 6 months during the study.

If one of the doses described in Table 2–1 is determined to be futile and is discontinued in MG0003, then that dose arm will be dropped from MG0007, and study participants in the affected dose arm will be transferred to an adjusted dose.

Dose modifications from 10mg/kg to 7mg/kg equivalent and vice versa are permitted at the beginning of the treatment cycles at the Investigator's discretion, and if the benefit-risk remains favorable for the study participant. Recommended dose modifications from 10mg/kg to 7mg/kg equivalent due to drug-related adverse events may include but are not limited to:

- Moderate to severe headaches that are considered to be related to rozanolixizumab
- Moderate to severe gastrointestinal (GI) disturbances that are considered to be related to rozanolixizumab
- Moderate to severe toxicities (\geq Grade 2 as defined by Common Terminology Criteria for Adverse Events [CTCAE], version 5.0) for which rozanolixizumab cannot be excluded as a cause
- Recurrent hypogammaglobulinemia with a serum total IgG level of <2 g/L.

Table 2–1: MG0007 dose levels and weight tiers

Bodyweight	Rozanolixizumab dose equivalent	
	7mg/kg Dose 1	10mg/kg Dose 2
≥35 to <50kg	280mg	420mg
≥50 to <70kg	420mg	560mg
≥70 to <100kg	560mg	840mg
≥100kg	840mg	1120mg

2.4 Determination of sample size

No formal sample size calculation can be performed. All eligible study participants from MG0003 and MG0004 will be invited to participate in MG0007. Approximately 200 study participants will be enrolled into MG0007.

The number of 200 study participants is assuming a drop-out rate from the lead-in study of approximately 15% (including participants who opt not to continue in MG0007).

3 DATA ANALYSIS CONSIDERATIONS

3.1 General presentation of summaries and analyses

For safety analyses, data will be summarized by dose levels of rozanolixizumab at the time of the event or measurement. For efficacy analyses, data will be summarized by the dose first received in the study. Additionally, efficacy data will be summarized by dose levels of rozanolixizumab received in each treatment cycle.

Statistical analysis and generation of tables, figures, participant data listings, and statistical outputs will be performed using SAS® Version 9.3 or higher. All tables and listings will use Courier New font size 9.

Descriptive statistics will be displayed to provide an overview of the study results. For continuous variables, descriptive statistics will include number of participants with available measurements (n), mean, standard deviation (SD), median, minimum, and maximum.

For categorical variables, the number and percentage of participants in each category will be presented. Unless otherwise noted, the denominator for percentages will be based on the number of participants included in the respective analysis set. Participants with missing data can generally be accounted for using the following approaches:

- For summaries of demographics and Baseline characteristics: summarize percentages based on all participants in the analysis set and include a “Missing” category (corresponding to participants with missing data for the variable being summarized) as the last row in the list of categories being summarized.
- For summaries of efficacy and safety endpoints, unless otherwise specified: summarize percentages based only on those participants with observed data for the variable being summarized. As the denominator may be different from the number of participants in the

analysis set being considered, the denominator should be displayed in the table. The general format for displaying this will be “n/Nsub (%).”

Unless otherwise noted, all percentages will be displayed to one decimal place. No percentage will be displayed for zero counts, and no decimal will be presented when the percentage is 100%.

For the purpose of the tabulations the lower and upper confidence limits for the percentages will be truncated at 0 and 100% respectively.

For PK concentration data, summary statistics will include geometric mean, geometric coefficient of variation (geoCV), 95% confidence interval (CI) for geometric mean, arithmetic mean, SD, median, minimum, and maximum.

Decimal places for descriptive statistics will always apply the following rules:

- “n” will be an integer;
- Mean (arithmetic, geometric), SD, and median will use one additional decimal place compared to the original data;
- geometric CV [%] will be presented with one decimal place;
- Minimum and maximum will have the same number of decimal places as the original value.

If no participants have data at a given visit, for example, then only n=0 will be presented. However, if 0<n<3, present the n, minimum and maximum only. If n=3, n, mean, median, minimum and maximum will be presented only. The other descriptive statistics will be left blank.

Derived variables in general will display the mean and median to 1 more decimal place, SD to 2 more decimal places and same decimal place to minimum and maximum than the variables used in the derivation. If the number of decimal places reported in the raw data is varied, then use either the maximum raw number of reported decimal places or 3, whichever is the lowest, as a guide for the descriptive statistics.

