2.1 Study rationale

MG0007 will complement the ongoing Phase 3 study, MG0003, and replace the open-label extension (OLE) study, MG0004. The study will evaluate the safety, tolerability, and efficacy of rozanolixizumab over the initial 6-week treatment cycle and subsequent treatment cycles when given as needed based on worsening of gMG symptoms. The study will gather information on the efficacy response of subsequent treatment cycles and the duration until next treatment is needed. The study will support the intended use of rozanolixizumab in study participants with gMG, (ie, repeated 6-week treatment cycles based on worsening of symptoms).

MG0003 is a Phase 3 study of rozanolixizumab in anti-acetylcholine receptor (AChR) or anti-muscle-specific kinase (MuSK) autoantibody-positive participants with gMG who experience moderate to severe symptoms and are being considered for additional treatment such as IVIg or PEX. The primary objective is to demonstrate the clinical efficacy of rozanolixizumab in study participants with gMG. The study consists of a Screening Period of up to 4 weeks, followed by a 6-week double blind Treatment Period, and a blinded Observation Period of 8 weeks. MG0003 will provide the core data to support marketing authorization application globally. The current OLE study, MG0004, is a Phase 3, randomized study to evaluate the long-term safety, tolerability, and efficacy of rozanolixizumab in study participants with gMG.

The MG0007 study has been designed with the following considerations:

1. Double-blind placebo-controlled data will be collected on a single cycle as part of the MG0003 study. MG0007 will provide data on subsequent treatment cycles when given as needed based on worsening of gMG symptoms.
2. An open-label design is deemed appropriate since a placebo controlled long-term extension study may raise ethical concerns.
3. The dose and treatment regimen for rozanolixizumab (equivalent to approximately 7mg/kg or 10mg/kg QW for 6-week treatment cycle) in MG0007 are identical to that used in MG0003.
4. For comprehensive data collection, an extended 16-week Observation Period was chosen to investigate maintenance of effect after a 6-week treatment cycle.

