9.5 MG-ADL responder rate (≥ 2.0 points improvement from Baseline)

Study participants will be classified as MG-ADL total score responders at a scheduled visit if there is an improvement (decrease of at least a 2-points) from Baseline in the MG-ADL total score.

The number and percentage of observed MG-ADL responders at each scheduled post-Baseline visit will be summarized by study cycle, actual dose level received within study cycle, and RLZ total using descriptive statistics.

Additional summary of observed MG-ADL responders by fixed dose and weight subgroups will also be conducted as specified in [Section 4.9.2](#).

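### Responder percentages at Days 71 to 155 leave out participants who have started a new cycle, and so overstate the share of treated participants still responding without one

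*SAP*

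**What the plan says.** The SAP's other efficacy endpoints include responder status over the Observation Period: "For each 6-week treatment cycle and Observation Period (where applicable), improvement from Baseline (Day 1) to each scheduled assessment" (SAP 2.2.2.2). SAP 9.5 plans the MG-ADL table accordingly: "The number and percentage of observed MG-ADL responders at each scheduled post-Baseline visit will be summarized by study cycle", split by the dose received in that cycle. SAP 9.7 and 9.8 do the same for QMG and MG-C.

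The denominator comes from SAP 3.1. The analysis set is the default, but for efficacy and safety endpoints the rule is to "summarize percentages based only on those participants with observed data for the variable being summarized". Because that number can differ from the analysis set, "the denominator should be displayed in the table", in the form n/Nsub.

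A participant leaves the Observation Period for a new cycle when symptoms worsen enough to need treatment, in the Investigator's judgement. SAP 2.3.1 gives the example of "an increase of 2.0 points on the MG-ADL or 3.0 points on the QMG scale". On timing it says: "The minimal time to start the next treatment cycle is 4 weeks following the last dose of the treatment period of the previous cycle". An earlier start is possible after discussion with the Medical Monitor.

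Protocol 2.1 gives the reason for the 16-week follow-up: the "Observation Period was chosen to investigate maintenance of effect after a 6-week treatment cycle".

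**The concern.** An observed-case percentage is harmless when absence from a visit has little to do with the outcome. Here the usual reason for having no Day 99 visit in a cycle is that the participant worsened and was retreated. Late-visit responder percentages are then computed in a group selected for not having needed another cycle. The Observation Period was designed to show how well the effect is maintained, and a reader will naturally take the Day 99 or Day 155 percentage as a statement about everyone treated in that cycle.

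The selection can also distort a comparison of doses. If one dose has many more restarts than the other, both columns can show the same percentage.

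**Working it through.** **1. Which visits are exposed.** Protocol Tables 1-2 and 1-3 put the last dose of a cycle at Day 36. The earliest usual restart is Day 36 + 28 = Day 64. The Observation Period visits are at Days 71, 99, 127 and 155, all later than Day 64. Day 43 is earlier, so it is essentially untouched. Day 71 is only 71 − 64 = 7 days after the earliest usual restart and should be the least affected of the four.

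**2. What happens to a restarted participant in the old cycle.**
- SAP 3.2.2 closes a cycle before the next one starts.
- SAP 3.2.1 applies no visit windows except for the premature end-of-treatment visit, so the new cycle's Day 1 score is not carried to a later visit of the old cycle.
- Protocol 9.2.1 does not impute missing values.
- SAP 3.9 lists two intercurrent events: rescue before Day 43, and permanent discontinuation due to a TEAE. Restart is not one of them.
- SAP 4.7 plans no sensitivity analysis.

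The participant therefore counts in neither n nor Nsub.

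**3. Size for the target of responding without a new cycle.** The documents give no responder rate or restart rate, so there is no plan figure to reproduce. Let N be the participants treated in the cycle and due for the visit, f the share restarted before it, and p the responder share among the rest. Assume nobody misses the visit for another reason.

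- Nsub = (1 − f)N and n = p(1 − f)N
- Planned percentage = n/Nsub = p
- Share responding without a new cycle = n/N = (1 − f)p
- Overstatement = p − (1 − f)p = f × p

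With p = 70% (assumed):

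| f (assumed) | Table shows | (1 − f) × 0.70 | Overstatement f × 0.70 |
|---|---|---|---|
| 20% | 70% | 56% | 14 points |
| 40% | 70% | 42% | 28 points |
| 60% | 70% | 28% | 42 points |

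Over assumed ranges of f from 20% to 80% and p from 60% to 80%, the excess runs from 0.20 × 0.60 = 12 points to 0.80 × 0.80 = 64 points. If 20% had restarted on one dose and 60% on the other, both columns would show 70%, against 56% and 28%.

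**4. A different target: the score the participant would have had without retreatment.** Let q be the responder share among restarted participants on that hypothetical score. The share over everyone is (1 − f)p + fq, and the difference from the planned figure is f(p − q). With f = 40%, p = 70% and q = 50% (all assumed) this is 0.40 × 0.20 = 8 points. It is zero if q = p and negative if q > p. The example trigger is a worsening between assessments, not a return to cycle Baseline. Someone 6 points better who then worsens by 2 is still 4 points better than Baseline, and still a responder. In an illustrative simulation with assumed linear loss of benefit and restart on a worsening of 2 points or more, the difference ran from about −4 to +10 points. For this target the sign is not fixed.

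**5. Overlap with SAP 9.11.** That section gives Kaplan-Meier estimates of time from last infusion to the next cycle, with restart as the event. From a Day 36 last dose, Days 99, 127 and 155 lie 63, 91 and 119 days later (one more under the SAP's plus-one convention). Estimates are planned at 60, 90 and 120 days. Day 71 lies 35 days later, between the planned estimates at 28 and 60 days.

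**The case against.** The strongest reply is that the plan already answers the duration question elsewhere. Protocol 9.4.1 names the time between cycles as the summary of how long the effect lasts. It is a secondary endpoint, while responder status in the Observation Period is only an other endpoint. As step 5 shows, the restart share at three of the four visits can nearly be read off SAP 9.11. This stands, and it limits the harm. But SAP 9.11 does not report responder status, and no planned table combines the two.

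A second reply is that nothing is hidden, because n/Nsub is printed and SAP 5.1 adds counts of participants by visit. That is true of the raw numbers. However, Nsub falls through restarts, missed visits, withdrawals and visits not yet due alike, and the table does not say which.

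A third reply is that a restarted participant has not necessarily lost response. That is correct (step 4). Counting restart as non-response is a choice of target and must be labelled as such.

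A reader might infer that the plan as a whole overstates maintenance of effect, that every missing value means the effect was lost, or that the rates will stay flat while most participants relapse. The documents support none of these. SAP 9.11 keeps restarted participants in its analysis, retreatment rests on the Investigator's judgement, and a flat 70% is an assumption. Participants who worsen but have not restarted stay in the denominator and pull the percentage down.

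Finally, all efficacy analysis is descriptive (SAP 9), so no test is affected.

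**Conclusion.** The point holds in a limited form. From Day 71 to Day 155, the planned MG-ADL, QMG and MG-C responder percentages describe participants not yet retreated in that cycle. Read as the share of treated participants responding without a new cycle, they are too high by f × p whenever anyone has restarted. That direction follows from the definitions. The size cannot be computed from the documents, and every percentage in the working rests on assumed inputs.

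The point does not reach the Day 43 secondary endpoints, and it is not a claim about scores in the absence of retreatment. Nor do the documents support treating every rescued or discontinued participant as a failure. Protocol 9.2.1 and SAP 3.9 analyse these responder endpoints under treatment policy regardless of rescue, and rescued participants can still be assessed. Some exits are administrative.

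**What to change.** In SAP 9.5, 9.7 and 9.8, keep the observed-case row. At each post-Day 43 visit where the scale is scheduled, add a supplementary row labelled as responding without a new cycle. MG-ADL is scheduled at all four visits. In subsequent cycles QMG and MG-C are scheduled only at Days 99 and 155 (Protocol Table 1-3).

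- **Denominator:** participants treated in that cycle who were due for the visit. Judge whether a visit was due from the cycle's Day 1, in the same way for restarted and other participants.
- **Restarted before the visit:** non-responder, with the number shown beside n/Nsub.
- **Rescued but still assessed:** observed status, in line with treatment policy.
- **Left out:** visits not yet due at the data cut, and administrative exits (transition to MG0020, product approval or managed access, and the 14-month limit in Denmark and the UK).
- **Missed visits:** a separate category. The SAP should also state where withdrawals for other reasons are placed.

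Add a footnote pointing to SAP 9.11 for time to restart. The restart dates are already derived for that section, so no new data and no change in trial conduct are needed. The cost is one row per responder table and a less favourable figure at late visits.
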